4.10.3.5 Overall Survival (OS)

OS is defined as the time from date of first dose until the date of death from any cause, regardless of whether the subject withdraws from therapy or received another anti-cancer therapy.

OS (months) = (date of death or censoring – first dose + 1) / (365.25/12)

Subjects who have not died by the analysis data cut-off date will be censored at their last date known to be alive before the cut-off date. Subjects known to be alive or dead after the data cut-off date will be censored at the data cut-off date. Subjects lost to follow-up will be censored at the date the subject is last known to have been alive.

Note: Survival calls will be made in the week following the date of DCO for the analysis, and if subjects are confirmed to be alive or if the death date is after the DCO date these subjects will be censored at the date of DCO. The status of ongoing, withdrawn (from the study) and “lost to follow-up” subjects at the time of the final OS analysis should be obtained by the site personnel by checking the subject’s notes, hospital records, contacting the subject’s general practitioner and checking publicly-available death registries. In the event that the subject has actively withdrawn consent to the processing of their personal data, the vital status of the subject can be obtained by site personnel from publicly available resources where it is possible to do so under applicable local laws.

For any OS analysis performed prior to the final OS analysis, in the absence of survival calls being made, it is necessary to use all relevant eCRF fields to determine the last recorded date on which the subject was known to be alive for those subjects still on treatment (since SURVIVE module is only completed for subjects off treatment if a survival sweep is performed). The last date for each individual subject is defined as the latest among the following dates recorded in the eCRF:

- AE start and stop dates
- Admission and discharge dates of hospitalization
- Study treatment date
- End of treatment date
- Laboratory test dates
- Date of vital signs
- Disease assessment dates on eCRF
- Start and stop dates of alternative anti-cancer treatment
- Date last known alive on survival status eCRF

- End of study date

The analysis of OS is based on the FAS. The number and percentage of subjects experiencing an OS event and Kaplan-Meier plots of OS will be presented. If subject numbers allow, the median OS and 2-sided 80% and 95% CI will be estimated using the Kaplan-Meier method.

Summaries of the number and percentage of subjects who have died, those still in survival follow-up, those lost to follow-up and those who have withdrawn consent will be provided.

A summary of the duration of follow-up for OS will be included using median (range). This will be presented separately for censored and non-censored subjects.

Duration of follow-up for OS is reported separately for censored subjects and non-censored subjects and is defined as follows:

Duration of follow-up for OS (months) = (date of death or censoring (date last known to be alive) – date of first dose + 1) / (365.25/12).

The proportion of subjects alive at every 3 months (3, 6, 9, 12) and associated 2 sided 80% and 95% CIs will be estimated using the Kaplan-Meier method.

Supportive data: Change in Target Lesion Tumour Size

Target lesions are measurable tumour lesions. Baseline is defined to be the last evaluable assessment prior to starting treatment.

Target lesion tumour size for the target measurable nodes and extra-nodal sites at any timepoint is defined as the sum of the product of the perpendicular diameters for multiple lesions. When a lesion is too small to measure, 5 mm x 5 mm will be assigned as the product of the perpendicular diameters.

If target lesion measurements are missing post-baseline, then the sum of the product of perpendicular diameters for multiple lesions will be set to missing for that post-baseline measurements. Subsequent percentage changes will consequently not be calculated using post-baseline measurements where any target lesion measurement is missing.

The percentage change in target lesion size at each timepoint for which data are available will be obtained for each subject, taking the difference between each timepoint and baseline multiplied by 100 (ie, [timepoint – baseline]/baseline x 100).

The best change in tumour size from baseline (ie, depth of response) is the largest decrease from baseline or the smallest increase from baseline in the absence of a reduction and includes all assessments:

- up to and including the first visit at which the overall visit response is a PD,
- prior to death in the absence of progression,
- prior to the start of subsequent anti-cancer therapy,
- or up to and including the last evaluable tumour assessment if the subject has not died, progressed, or stated subsequent anti-cancer therapy.

Only response-evaluable subjects with measurable disease at baseline and at least one post baseline tumour assessment should be included in summaries of best percentage change in tumour size (measurable disease is as denoted on the CRF by the investigator).

The target lesion size and percentage change from baseline in target lesion size will be summarised using descriptive statistics and presented at each scheduled timepoint (refer to efficacy naming conventions in [Section 4.2](#)). Subjects who progress before the scheduled assessment at 8 weeks should have had a tumour assessment performed at the time of progression prior to treatment discontinuation. The tumour size from their latest progression assessment is used instead of the Week 8 assessment for these subjects.

Additionally, using scheduled and unscheduled tumour assessments ‘spider’ plots of percentage change from baseline in target lesion size by subject will be presented. A graphical summary of the best percentage change in the target lesion tumour size will be presented in a vertical bar chart with each subject’s best percent change from baseline to nadir displayed as a vertical bar, with color coding that indicates best response attained (‘waterfall’ plot).

Supportive analysis:

As supportive analysis, the efficacy outcomes (ORR, CR and PR) may be presented by other relevant subgroups defined by AZ medical. This may include lymphoma classification, histology subtype, COO (GCB/non-GCB), prior CAR-T, BiTE and/or BTKi therapies.

4.10.4 Pharmacokinetics

4.10.4.1 Pharmacokinetic Concentrations

Plasma concentrations of AZD4573 plus acalabrutinib and its metabolite ACP-5862 will be listed by actual and relative (to dose administration) sampling time. Data from subjects excluded from the PK analysis set (ie, Safety Analysis Set) will be included in the data listings, but not in the descriptive statistics or in the inferential statistics. The following summary statistics will be presented for these concentrations and PK parameters at each time point by dose level:

- n below LLOQ (only for concentrations)
- Geometric Mean (gmean, calculated as $\exp[\mu]$, where μ is the mean of the data on a logarithmic scale)
- Geometric CV% (gCV, calculated as $100 \sqrt{[\exp(s^2)-1]}$, where s is the standard deviation of the data on a log scale)
- Gmean + gSD (gSD calculated as $\exp[\mu \pm s]$)
- Gmean – gSD
- Arithmetic Mean
- Arithmetic Std Dev
- Minimum
- Median
- Maximum

- Number of observations

In listings, concentrations below the lower limit of quantification (LLOQ) will be presented as NQ. In listings and tables where the terms BLQ or LLOQ are included, the LLOQ (numerical value) will be included in a footnote.

For the calculation of statistics, concentrations that are BLQ will be handled as follows at each time point:

- If $\leq 50\%$ of the concentrations are BLQ, all BLQ values will be set to the LLOQ, and all descriptive statistics will be calculated.
- If $>50\%$, but not all, of the concentrations are BLQ, the geometric mean, geometric CV, arithmetic mean, and arithmetic Std Dev will be reported as 'NC' (not calculable). The maximum value will be reported from the individual data, and the minimum and median will be set as 'BLQ'.
- If all concentrations are BLQ, no descriptive statistics will be calculated. 'NA' (not applicable) will be presented for geometric CV, and arithmetic Std Dev, and 'BLQ' will be presented for geometric mean, arithmetic mean, median, minimum, and maximum.

For PK concentration and parameter data, if there are <3 values available at a time point, only the maximum, minimum, and n will be reported; the remaining descriptive statistics will be reported as 'NC'. Concentrations that are BLQ are considered a value.

Missing samples will be reported as no sample ("NS") and excluded from analysis.

Source data shall be used in all derived PK concentrations without prior rounding.

The following figures, in black and white, will be generated for each of AZD4573, acalabrutinib and its metabolite ACP-5862:

- Subject Profiles, Plasma Concentration Time Data – Linear Scale
- Subject Profiles, Plasma Concentration Time Data - Semi-Logarithmic Scale
- Gmean (\pm gSD), Plasma Concentration Time Data
- GMean, Plasma Concentration Time Data - Semi-Logarithmic Scale

Individual figures will be plotted using concentration versus actual time, and mean figures will be plotted using concentration versus nominal time, by treatment or dose level and cycle/PK day, as needed.

4.10.4.2 Pharmacokinetic Parameters Calculation and Summary

Derived PK parameters will be summarized by cycle, separately by dose levels. The following summary statistics will be presented for the estimated PK parameters, as appropriate:

- Gmean (calculated as $\exp[\mu]$, where μ is the mean of the data on a logarithmic scale)
- gCV (calculated as $100 \sqrt{[\exp(s^2)-1]}$, where s is the standard deviation of the data on a log scale)
- Gmean + gSD (gSD calculated as $\exp[\mu \pm s]$)

- Gmean - gSD
- Arithmetic mean calculated using untransformed data
- Standard deviation calculated using untransformed data
- Minimum
- Median
- Maximum
- Number of observations

The following rules will be followed with regards to the number of decimal places and presentation of data in the tables and listings for PK parameters:

- Individual PK parameters will be presented to four significant digits, with the exception of t_{max} , which will be presented to two decimal places.
- Parameters derived directly from source data (eg, C_{max} ,) shall be reported with the same precision as the source data (if this is not four significant digits).
- The mean, geometric mean, median and Std Dev values will be reported to four significant digits, all other descriptive statistics will be reported to three significant digits except for $CV\%$ which will be presented to one decimal place.
- For t_{max} the minimum and maximum will be presented to two decimal places and all other descriptive statistics will be presented to three decimal places.
- Estimates and confidence intervals in the form of percentages will be presented to two decimal places.

Criteria for Handling Concentrations Below the Limit of Quantification or Missing Concentrations in Pharmacokinetic Analysis

For the non-compartmental analysis (NCA) and individual plot, if a BLQ value occurs before the first measurable concentration, it will be assigned a value of 0, otherwise it will be treated as missing. The following rules apply with special situations defined below:

- Where two or more consecutive concentrations are BLQ at the end of a profile, the profile will be deemed to have terminated and any further quantifiable concentrations will be set to missing for the calculation of the PK parameters unless they are considered to be a true characteristic of the profile of the drug.
- If an entire concentration-time profile is BLQ, the profile will be excluded from the PK analysis.
- If a pre-dose measurement for the first dose of Cycle 1 is missing, the value will be set to zero.

Treatment of Outliers in Pharmacokinetic Analysis

If a value is considered to be anomalous due to being inconsistent with the expected PK profile, it may be appropriate to exclude this point from the PK analysis. However, the exclusion of data must have strong justification and will be documented in CSR.

Quantifiable pre-dose concentration values in the first dosing of Cycle 1 will be considered anomalous and set to missing for the PK analysis.

4.11 Safety and Tolerability Evaluation

Module 1:

Safety, tolerability and DLT data will be listed and summarised as defined by the current AZ standards (oncology early phase study outputs).

The Safety analysis set will be used for all safety and tolerability analyses. All listings and tables, other than those to assess DLTs will be based on the Safety Analysis Set. To describe the DLTs during Cycle 1 in Part A, the DLT-evaluable Analysis Set will be used. To describe DLT-like events beyond Cycle 1 all subjects who receive any amount of study treatment after Cycle 1 will be included.

Module 1 Parts A and B include AEs, AESIs, DLTs in Module 1 Part A Cycle 1, DLT-like events outside of the dose-setting evaluation period, laboratory data, vital signs, and ECGs as safety assessments. In Module 1 Part A, the safety assessments, which also include Cycle 1 DLTs for dose setting, are primary endpoints. In Module 1 Part B, the safety assessments are a secondary endpoint. Listings and summary tables and figures of all safety data for Module 1 Part A and Part B will be created as described in this section. In addition, for Module 1 Part A dose setting MTD (if determined) will be reported.

Module 2:

For Module 2 subjects, all safety data will be presented in separate listings and no summary tables will be provided.

The by subject listing will include the identification of the treatment period (Period 1/ Period 2) when the event occurred and/or the safety assessment was performed.

4.11.1 Exposure and treatment administration

Module 1:

Exposure amounts, durations and dose modifications and interruptions/delays will be summarised for the following periods:

- Overall treatment period
- Cycle 1
- Up to first tumour assessment
- Cycle 2 onwards

Duration of AZD4573 exposure is defined by the last date of actual AZD4573 dosing (ie, a dose > 0 mg was given) plus 6 days (due to the fact that AZD4573 is ordinarily dosed on a weekly schedule) minus the date of first AZD4573 dose (> 0 mg) plus 1.

- For subjects who die whilst on study treatment or if a DCO occurs, duration of exposure (months/weeks) is defined as date of death/DCO (whichever occurs first) minus the date of first treatment plus 1 day.
- Therefore: Duration of exposure of AZD4573 (weeks) = [min (last dose date where dose > 0 mg + 6, date of death, date of DCO) – first dose date + 1]/7.

Actual duration of exposure (weeks) = [duration of exposure (days) – total duration of dose delays (days)]/7. Duration of exposure is calculated as above, and dose delays are defined as any length of time where the subject has not taken any of the planned dose in accordance with the protocol. The actual exposure calculation makes no adjustment for any dose reductions that may have occurred.

Duration of dose delays of AZD4573 will be derived for doses indicated as being delayed on the eCRF for subjects enrolled on CSP v3.0 and later versions. For each individual dose, the duration of dose delay is the number of days the dose was received outside of the original planned dosing schedule. Overall duration of dose delays will be calculated as the sum of all individual dose delays during the study. For example, assume the eCRF indicate that there was a treatment delay (question “Treatment delayed” indicated as “Y” by investigator) then the duration of the individual delay will be [date first dose received after delay – date last dose received before delay – 9]. 9 is being used to account for the 2-day window. For example, if dose is given on days 1 and 15 with the eCRF indicating a delay, the duration of the delay = 15 – 1 – 9 = 5 days.

The number of subjects with dosing delays and total dose delays will be summarised. Dose delays will also be summarised for number of delays with a duration < 7 days and number of delays with a duration \geq 7 days.

- Duration of acalabrutinib exposure is defined by the last date of actual acalabrutinib dosing (ie, a dose > 0 mg was given) minus the date of first dose (> 0 mg) plus 1.
 - Duration of exposure acalabrutinib (weeks) = [min (last dose date where dose > 0 mg, date of death, date of DCO) – first dose date + 1]/7.
 - Actual duration of acalabrutinib exposure is the sum of duration of exposure – total duration of dosing delays.

Total and actual treatment duration will be summarised by descriptive statistics for each study drug (AZD4573 and acalabrutinib) and dose level/cohort, separately for Cycle 1 (including ramp-up) and for other treatment cycles. In addition, the number and percentage of subjects with at least one dose interruption will be summarised separately for Cycle 1 (including ramp-up) and for other treatment cycles, for each study drug. Exposure swimmer plot(s) will be produced, with a line presented for each subject to display relevant exposure and disposition details.

Dosing deviations for study intervention (s) will be summarized with reasons for deviations for the following categories: reductions and interruptions.

The following additional summaries will also be produced:

- Number of subjects that completed Cycle 1 (ending a week after receiving 12 mg AZD4573 for three times), including number of subjects that did not complete Cycle 1.
- Number of doses received per subject in Cycle 1.
- Total and actual duration of exposure, specific to Cycle 1.
- Number of subjects that initiated Cycle 2.

Module 1 Part A:

- Number of subjects that completed DLT evaluability period (all doses up to 3rd dose at target level), and number of subjects that did not complete DLT evaluability period
- Number of doses received per subject in DLT evaluability period (including subjects that did not complete DLT evaluability period)
- Actual treatment duration in weeks of exposure specific to DLT evaluability period (including subjects that did not complete DLT evaluability period)
- Number of subjects that initiated Post DLT Evaluability Period

Missed or forgotten doses

Missed and forgotten doses will be included in the listings for dosing but will not be included as dose interruptions in summary tables. However, missed doses will be included in the calculation of actual treatment duration.

Module 2:

For Module 2 subjects, actual and planned doses of AZD4573 and acalabrutinib will be appropriately listed by identifying the treatment period (Period 1/Period2) when the actual administration occurred.

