The calculation of RDI for AZD4573 is illustrated with the following example. Assume a subject receives final dose of AZD4573 on Study Day 85. This subject was therefore 12.1 weeks (85/7) on treatment. The intended number of doses is therefore 13. From the above formula $D = 6 + 9 + (12 \times 11) = 147$ mg. Assume the actual doses received by the subject is 6, 0, 6, 9, 12, 12, 12, 12, 0 and 12. From the above formula, $d = 81$ mg. RDI for the overall treatment period is therefore $100\% \times 81/147 = 55.1\%$. For the RDI in Cycle 1, $d = 6 + 6 + 9 + 12 + 12 = 45$ (Cycle 1 ends after receiving the 5th dose of AZD4573), and $D = 6 + 9 + (12 \times 3) = 51$. The RDI in Cycle 1 is therefore $100\% \times 45/51 = 88.24\%$.

The following summaries will be produced:

- Summary of Interruptions (including duration of interruptions) and reductions of IP
- Summary of RDI
- Summary of intended and actual exposure AZD4573

Module 2:

The RDI will not be calculated and not presented for Module 2 subjects.

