4.11.3 Dose limiting toxicities (DLTs)

Module 1:

DLTs contributing to dose setting in Module 1 Part A Cycle 1 will be listed and summarised separately from AEs which meet the DLT definition criteria but are presented after the initial DLT setting assessment period in Module 1 Part A or in Module 1 Part B (DLT like-events).

The DLT criteria are defined in Section 15.3 of the CSP.

The number of Module 1 Part A dose-setting subjects evaluable for determination of DLTs during the DLT-assessment period and the number of subjects with any DLT will be summarised by dose level. For analysis reporting purposes, the DLTs are as approved and documented at the Safety Review Committee meetings. Excel spreadsheet created manually from the SRC meeting minutes and checked independently by another individual will be shared with the “DLT Evaluability =Y/N” information. The MTD will be selected from all tried dose levels that have not been previously declared to be unsafe with a DU decision according to the mTPI-2 algorithm (see CSP Section 15.2). With this constraint, the MTD will be determined as the dose level with the DLT estimate closest to the target toxicity level of 30%. The MTD will be determined by isotonic regression analysis applied to DLT rates observed in the DLT-assessment period during dose exploration using the mTPI-2 method. In the case of dose levels with estimated toxicity of equal distance (tied dose levels) from the target toxicity of 30%, the following approach is used: among all tied dose levels the highest dose level with target toxicity $\leq 30\%$ will be selected, unless all tied dose levels have estimated toxicity $> 30\%$, in which case the lowest dose level will be selected.

For Module 1 Part B subjects in meeting the same criteria for DLT evaluability that were used for Module 1 Part A dose setting, the number and percentage with any DLT-like event reported as an adverse event, will be summarised.

For pooled RP2D-treated Module 1 Part A and Part B subjects that received 3 AZD4573 doses at target level, the number and percentage that experienced at least one DLT-like event reported as an adverse event after receiving any further amount of study treatment will be summarised.

Types of DLTs and DLT-like events and numbers of events per subject will also be summarised.

Module 2:

This section is not applicable to Module 2 subjects.

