6 APPENDICES

Module 1 - Part A subjects to be included in Part B analysis

PURPOSE:

This document describes the process for using data from subjects enrolled in Module 1 Part A in analyses for Module 1 Part B. This document describes:

- the process for Cell of Origin (COO) testing, used to identify GCB and non-GCB DLBCL subjects;
- the selection criteria for Part A subjects whose data will be included in the final analysis for Part B;
- the process to document the recycling of Part A subjects data.

PROCESS

1. Cell of Origin (for all part A and part B subjects)

For the purposes of recycling of data from Part A subjects for analysis with Part B subjects data, COO data from local assessment will be used.

2. Definition of Part A subjects that will be included in the Module 1 Part B final analysis

Data from Module 1 Part A subjects will be analysed together with data from Part B subjects if the Part A subjects fulfil all the conditions below:

- Must have received any amount of AZD4573 and acalabrutinib on study;
- Must have been enrolled in the 12 mg (RP2D) dose level cohort;
- Must have a diagnosis of de novo DLBCL, ie:
 - DLBCL NOS (de novo), or
 - High-Grade B cell Lymphoma (NOS), or
 - High-Grade B cell Lymphoma with MYC and BCL2 and/or BCL6 rearrangements;
- Must have measurable disease at baseline (ie be part of the response evaluable set).

3. Documentation of review and confirmation

The Parexel Programming team will programmatically identify Part A subjects whose data can be recycled in Part B for final analysis purposes, based on the criteria described in this document.

Subjects that can be recycled will be marked by population flags in the ADAM and SDTM specifications. TFLs will be generated including the correct individuals (including recycled subjects) in each cohort; a listing of recycled subjects will also be included in the TFLs.

SIGNATURE PAGE

This is a representation of an electronic record that was signed electronically and this page is the manifestation of the electronic signature

Document Name: d8230c00002-sap-ed-5		
Document Title:	Statistical Analysis Plan Edition 5	
Document ID:	Doc ID-004599196	
Version Label:	5.0 CURRENT LATEST APPROVED	
Server Date (dd-MMM-yyyy HH:mm 'UTC'Z)	Signed by	Meaning of Signature
30-Oct-2023 14:53 UTC	PPD 	Content Approval

Notes: (1) Document details as stored in ANGEL, an AstraZeneca document management system.

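### The SAP ends Cycle 1 at two different points, and the one in Section 4.11.1, fixed at 12 mg, cannot be reached by a Part A cohort with a lower target dose

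*SAP*

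**What the plan says.** The SAP places the end of Cycle 1, or of the period it treats as equivalent, in three ways.

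- **Section 4.11.1, Module 1 list (both Parts):** "Number of subjects that completed Cycle 1 (ending a week after receiving 12 mg AZD4573 for three times". This is an absolute dose. It stands before the separate Part A list, and Section 4.2 presents Module 1 tables by dose level.
- **Section 4.11.2, dose-intensity example:** "Cycle 1 ends after receiving the 5th dose of AZD4573". This counts administered doses, whatever their size.
- **Section 4.11.1, Part A list:** "Number of subjects that completed DLT evaluability period (all doses up to 3rd dose at target level". This is relative to each subject's target and agrees with the DLT-evaluable definition in Section 4.5, Table 2. Section 4.11 describes Part A DLTs in Cycle 1 using that same set.

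Several outputs depend on the boundary. Section 4.11.1 states: "Exposure amounts, durations and dose modifications and interruptions/delays will be summarised for the following periods", and the list includes Cycle 1 and Cycle 2 onwards. The same section counts the doses given in Cycle 1 and the subjects who start Cycle 2, and splits treatment duration and interruptions between Cycle 1 and the other cycles. Section 4.11.2 illustrates a Cycle 1 RDI. Section 4.11 adds: "To describe DLT-like events beyond Cycle 1 all subjects who receive any amount of study treatment after Cycle 1 will be included".

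Part A has more than one dose level. Section 4.11.3 says "The MTD will be selected from all tried dose levels that have not been previously declared to be unsafe", and the Appendix on reuse of Part A data requires "Must have been enrolled in the 12 mg (RP2D) dose level cohort".

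**The concern.** A fixed 12 mg criterion cannot mark completion of a cycle in a part of the study that runs several target doses. A subject assigned a lower target who follows the plan perfectly never receives 12 mg, so the completion count is zero for that cohort whatever happened. A 12 mg subject reduced before the third 12 mg dose is also counted as never completing, however many doses follow.

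The fifth-dose rule does not settle the matter. It is a different rule, it appears only inside a worked example, and nothing says which of the two governs. Two programmers could split the same subject's exposure at different doses and both be following the SAP.

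At stake is the tolerability description by dose level, which belongs to the primary objective of Part A. A table showing that nobody in a lower-dose cohort finished Cycle 1 would report the wording of the rule, not the subjects' experience.

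**Working it through.** **1. Reproduce the SAP's own figures (Section 4.11.2).** The listed doses are 6, 0, 6, 9, 12, 12, 12, 12, 0, 12 mg.

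- Delivered: d = 6 + 0 + 6 + 9 + 12 + 12 + 12 + 12 + 0 + 12 = 81 mg.
- Intended: D = 6 + 9 + (12 × 11) = 147 mg.
- Overall RDI = 100 × 81/147 = 55.1%, as stated.
- Cycle 1 by the fifth-dose rule: the first five administered doses are 6, 6, 9, 12, 12, so d = 45. The intended dose is 6 + 9 + (12 × 3) = 51. RDI = 100 × 45/51 = 88.24%, as stated.

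**2. Apply the Section 4.11.1 rule to the same subject.** The five doses that close Cycle 1 in the example contain only two 12 mg doses. The third 12 mg dose is the sixth dose administered.

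- Delivered to that point: 6 + 6 + 9 + 12 + 12 + 12 = 57 mg.
- If the intended dose stays at 51 mg, RDI = 100 × 57/51 = 111.8%, against the stated 88.24%. The SAP does not give an intended dose for this longer interval, so no single correct value can be quoted under the 12 mg rule.

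The rules therefore differ by one dose and 57 − 45 = 12 mg, for a subject receiving 12 mg.

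**3. Compare the rules by target dose.** The entry is the administered dose at which the criterion is met. The Section 4.11.1 completion rule then adds one week. The lower-target sequences are assumptions, because the SAP does not give the Part A ramp-up schedules.

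| Sequence (mg) | Three 12 mg doses | Fifth dose | Three doses at target |
|---|---|---|---|
| 12 mg target, as planned: 6, 9, 12, 12, 12 | 5 | 5 | 5 |
| 12 mg target, SAP example: 6, 6, 9, 12, 12, 12 | 6 | 5 | 6 |
| 9 mg target (assumed): 6, 9, 9, 9, 9 | never | 5 | 4 |
| 6 mg target (assumed): 3, 6, 6, 6, 6 | never | 5 | 4 |

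If a lower cohort had two ramp-up doses instead of the one assumed, its third target dose would be dose 2 + 3 = 5. The last column for those rows then ranges from 4 to 5. The entry of never does not change.

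**4. Are there cohorts below 12 mg?** The SAP does not list them. It refers to several tried dose levels and to the 12 mg cohort as one of them. Table 5, headed as examples, has no preparation above 12 mg, and it includes 1.5 mg and 3 mg, which the 6/9/12 mg ramp-up does not use. The inference is strong, but it remains an inference.

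**5. Which outputs move?** Those split at the end of Cycle 1:

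- counts of subjects completing Cycle 1 and starting Cycle 2;
- doses and exposure duration in Cycle 1 against later cycles;
- modifications, interruptions and delays by period;
- Cycle 1 RDI;
- the Section 4.11 set treated after Cycle 1, used for DLT-like events.

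Only the completion count carries the 12 mg wording itself. The others are affected to the extent that this boundary is used for them.

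**The case against.** The best defence is that the 12 mg wording is a parenthesis on one descriptive count. The count of subjects starting Cycle 2 has no such condition, visits from Cycle 2 are named by the protocol schedule (Section 4.2), and a lower-target subject can reach the fifth-dose rule. Part A also has its own target-based summaries, including "Number of subjects that initiated Post DLT Evaluability Period". No hypothesis is tested.

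Much of this stands, and it rules out stronger readings that a reader might infer:

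- **Lower-dose subjects vanish from all later safety summaries.** They do not. Outside the DLT tables, safety outputs use the Safety Analysis Set (Section 4.11), and Part A safety data are pooled over cycles (Section 3.3.3). Exposure overall and up to the first tumour assessment does not use the boundary.
- **Later DLT-like events are lost because of the 12 mg wording.** Section 4.11.3 bounds these events by the DLT assessment period. Its later-event summary is restricted by design to RP2D subjects with three target-level doses. Only the broader set in Section 4.11 depends on where Cycle 1 ends, and the SAP gives no counts from which to size a bias in event rates.
- **MTD selection is distorted.** It uses DLTs documented by the Safety Review Committee in a set already tied to target dose.
- **The 12 mg visit names are wrong for lower cohorts.** Section 4.2 names Cycle 1 visits by the amount received, so a 9 mg subject is already named correctly, and the windows in Section 4.3.2 are examples.

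The defence does not remove the conflict. The SAP states two end-points for Cycle 1, they give different answers in its own example, and it does not say which one governs. A cycle definition in the protocol would still leave at least one SAP statement to correct.

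**Conclusion.** The point holds as an inconsistent definition with limited reach. Section 4.11.1 and Section 4.11.2 end Cycle 1 at different doses, and the Section 4.11.1 wording does not fit dose levels below 12 mg.

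Its size is 0 of n Cycle 1 completers in any Part A cohort with a lower target, and a one-dose, 12 mg difference in the SAP's own example: 45 mg against 57 mg delivered, or 88.24% against 111.8% with the denominator kept at 51 mg. The first figure rests on the inference that such cohorts exist and on a literal reading of the count. The second rests only on the SAP's numbers and on keeping its denominator.

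The effect is confined to descriptive outputs split at the end of Cycle 1. It is worth correcting because those outputs describe tolerability by dose level, and the present rule can produce a wrong count, not merely an unspecified one.

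**What to change.** State one analysis definition of the end of Cycle 1 for Module 1 that works at every dose level, and use it throughout Sections 4.11, 4.11.1 and 4.11.2. One candidate is 7 days after the third AZD4573 dose at the subject's assigned target level. It matches the target-based DLT period and leaves the planned 12 mg sequence unchanged, with the third target dose still at dose 5.

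Add a data rule for subjects reduced before that point, such as the recorded Cycle 2 Day 1. Then correct the Cycle 1 RDI example to match, stating both the delivered and the intended dose for the chosen interval.

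This defines an analysis boundary only and changes no dosing. The cost is a wording amendment and one derived date in programming, with no new data. The visit names can stay as they are.
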